Study Protocol

Official Title: Visceral Manipulation in Patients With Chronic Low Back Pain

NCT03101020

Document Date: November, 18th 2016

Study Protocol

[figure not shown]
All participants received equal treatment during the assessments and conventional therapy. They were treated one time per week for five weeks. Each session took 50 minutes, starting with 40 minutes of conventional physiotherapy and finishing with 10 minutes of active or placebo visceral manipulation, depending on the participant's group allocation.

Conventional physiotherapy

[figure not shown]
We created a protocol of exercises for individuals with low back pain based on the clinical practice guidelines by Delitto *et al.* (2012). The protocol consisted of general exercises to mobilize, strength, and stabilize the spinal column, pelvis and hip, as it is described at Figure 1. All participants were oriented to keep an active lifestyle focusing on the activities they could perform (Koes *et al.* 2010; Panagopoulos *et al.* 2014).

At the end of the first session, the participants received a list with the description and photos of the exercises they performed during that session and that they would need to do every other day at home; however, there was no control if the participants performed the exercises at home. The criteria to progress the exercises were no pain, no fatigue, and no fear on performing it.

[figure not shown]
A

B

[figure not shown]
C

[figure not shown]
D

E (1)

E (2)

F (1)

[figure not shown]

F (2)

[figure not shown]

F (3)

[figure not shown]
G (1)

G (2)

[figure not shown]
G (3)

H (1)

H (2)

[figure not shown]
I (1)

I (2)

[figure not shown]
J (1)

J (2)

[figure not shown]
J (3)

K (1)

K (2)

L (1)

L (2)

Figure 2. Exercise protocol. **A** Erector spinae stretching, in dorsal decubitus pull the knee towards the abdomen – 2 sets of 30 seconds. **B** Knee rolls, roll the knees to one side and the other maintaining both shoulders on the floor – 2 sets of 10 seconds per side. **C** Piriformis stretch, in dorsal decubitus cross one ankle over the opposite knee and pull this leg towards the abdomen – 2 sets of 30 seconds per side. **D** Pelvic tilts, perform pelvic anteversion and retroversion – 10 to 15 repetitions. **E(1)** Back extensions, in ventral decubitus, extend the back supporting the upper body on flexed

elbows – 10 to 15 repetitions. **E(2)** Back extensions progression, the same position but supporting the upper body on the hands with the elbows extended. **F(1)** Activation of abdominal muscles, in dorsal decubitus perform isometric contraction of the profound abdominal muscles during breathing – 3 sets of 10 breathings. **F(2)** Activation of abdominal muscles progression 1, the same exercise but lifting a flexed knee in the air and maintaining it steady during the set – 2 sets of 10 breathings per side. **F(3)** Activation of abdominal muscles progression 2, the same exercise but lifting an extended knee in the air and maintaining it steady during the set – 2 sets of 10 breathings per side. **G(1)** Activation of back and hip muscles, in side lying, perform isometric contraction of unilateral back and hip muscles during breathing – 3 sets of 10 breathings. **G(2)** Activation of back and hip muscles progression 1, the same exercise but lifting a flexed knee and maintaining the ankle together and the leg steady during the set – 2 sets of 10 breathings per side. **G(3)** Activation of back and hip muscles progression 2, the same exercise but lifting an extended knee and maintaining it steady during the set – 2 sets of 10 breathings per side. **H(1)** Bridge exercise – 3 sets of 10 repetitions. **H(2)** Bridge progression, perform a single leg brig exercise – 3 sets of 10 repetitions per side. **I(1,2)** Quadruped Cat and Camel exercise – 10 to 15 repetitions. **J(1)** Single arm or leg raise, in quadruped position raise all limbs (arms and legs) one at a time and maintain the position – 1 set of 30 seconds for each limb. **J(2)** Quadruped opposite arm and leg raise exercise progression – 2 sets of 30 seconds per side. **K(1)** Plank, perform the plank exercise supporting the lower body on the knees – 2 sets of 30 to 60 seconds. **K(2)** Plank progression, perform the plank exercise supporting the lower body on the feet – 2 sets of 30 to 60 seconds. **L(1)** Side plank, perform the side plank exercise supporting the lower body on the knees – 2 sets of 30 to 60 seconds. **L(2)** Side plank progression, perform the side plank exercise supporting the lower body on the feet – 2 sets of 30 to 60 seconds.

Visceral manipulation

During all sessions, the participants had to remain in a hook-lying position and the head over a pillow to decrease the tension on the abdominal wall. A well-trained physiotherapist performed the visceral manipulation over eight spots on the abdomen. Each spot has a specific technique name, which are described in Figure 2, and each technique took 1 minute, except for the last two techniques that were performed 10 times each. For the experimental group (direct visceral manipulation), the therapist performed a deep pressure with the lower palm over those spots. The placebo visceral manipulation involved a light touch over the same spots, without intending to treat the patient, with the same amount of time and repetitions as the experimental group (McSweeney et al. 2012). At the end of the last session, the participants were asked to identify if the technique they received was the experimental or the placebo one.

[figure not shown]

Figure 3. Visceral manipulation protocol. Orientation of the pictures, cranial to the left and caudal to the right. **A** Cardia manipulation – 1 minute. **B** Pylorus manipulation – 1 minute. **C** Oddi sphincter manipulation – 1 minute. **D** Duodeno-jejunal valve manipulation – 1 minute. **E** Ileocecal valve manipulation - 1 minute. **F** Sigmoid colon manipulation – 1 minute. **G** Liver global manipulation – 10 repetitions. **H** Global hemodynamic manipulation – 10 repetitions with pressure during expiration and another 10 for inspiration.

Outcomes

All participants were assessed three times, pre-treatment, post-treatment and follow-up. Pre-treatment assessment was one week before the first session of treatment, post-treatment was right after the last session of treatment and the follow-up was one week after the last session of treatment. A team member, which was not involved with the interventions, was responsible for collecting all the baseline measures and outcomes.

Primary outcome

Pain intensity was evaluated through a Visual Analog Pain Scale of 11 points, where the participant choose a number from 0 to 10, 0 equals to “no pain at all” and 10 to “unbearable pain” (Childs *et al.*, 2005).

Secondary outcomes

Lumbar spine mobility was assessed through the original Schober Test. Roland-Morris Disability Questionnaire was used for General functionality and Patient Specific Functional Scale was used for Specific functionality (Tousignant *et al.* 2005; Nusbaum *et al.* 2001; Kowalchuk-Horn *et al.*, 2011; Oliveira *et al.*, 2008; Stratford *et al.*, 1995).

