Statistical Plan

Official Title: Visceral Manipulation in Patients With Chronic Low Back Pain

NCT03101020

Document Date: November, 18th 2016

Statistical Analysis Plan

Intention to treat analysis was employed when necessary, with the data from the previous evaluation repeated to substitute missing data. The Kolmogorov-Sirmonov test demonstrated normal data distribution. Thus, parametric tests were performed and the data were expressed as mean and standard deviation. Two-way analysis of variance (ANOVA) was used to compare the effects of stimulation during motor training on the main outcome variables and the Bonferroni correction for multiple comparisons was employed as the post hoc test. The dependent variables were pain intensity, lumbar mobility, general functionality and specific functionality. The independent fixed variables were treatment (baseline, posttreatment and follow-up), group (experimental group and control group) and group-treatment interaction. The Pearson correlation test verified the correlation between the outcomes of the variables. A p-value <0.05 indicated a statistically significant result. The data were organized and tabulated using the Statistical Package for Social Sciences (v.19.0).

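### No pain rating is planned for 35 days although participants attend weekly, so anyone lost before the end of session 5 and not recalled is entered as unchanged from before treatment

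*Protocol*

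**What the plan says.** The opening paragraph of the protocol sets the treatment schedule: "They were treated one time per week for five weeks". The Outcomes section allows three assessments: "All participants were assessed three times, pre-treatment, post-treatment and follow-up". On the timing of the first two it says "Pre-treatment assessment was one week before the first session of treatment, post-treatment was right after the last session of treatment". For the third, the section adds a separate date: "the follow-up was one week after the last session of treatment". The primary outcome needs a single number: "Pain intensity was evaluated through a Visual Analog Pain Scale of 11 points, where the participant choose a number from 0 to 10". No rating is described at sessions 1 to 4 or on arrival at session 5. Outcome collection is kept apart from treatment: "A team member, which was not involved with the interventions, was responsible for collecting all the baseline measures and outcomes".

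The SAP handles missing values "with the data from the previous evaluation repeated to substitute missing data", and its model has three time levels: "The independent fixed variables were treatment (baseline, posttreatment and follow-up), group (experimental group and control group) and group-treatment interaction".

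Neither document gives a sample size, standard deviation, target difference or expected dropout. Neither says whether someone who stops attending is still recalled for the post-treatment and follow-up assessments.

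**The concern.** A participant can attend three or four sessions, stop, and leave a record holding only a score taken a week before treatment began. The SAP then copies that score into both later time points, so the analysis treats the person as having had no change in pain.

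This is not only an objection to carry-forward. If people leave because of how their pain is going during the course, a better analysis of the three planned assessments still cannot condition on that pain, because it was never written down. At stake is the between-group difference on the primary outcome. The missing information could be had for one number at visits that already take place.

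**Working it through.** **1. Schedule.** Take session 1 as day 0.

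| Event | Day |
|---|---|
| Pre-treatment rating | -7 |
| Sessions 1 to 5 | 0, 7, 14, 21, 28 |
| Post-treatment rating (after session 5) | 28 |
| Follow-up rating | 35 |

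Unrated interval: 7 + 4 × 7 = 35 days, of which 28 lie between session 1 and session 5. With arrival ratings at sessions 2-5, the rating days become -7, 7, 14, 21, 28 (arrival), 28 (after the session) and 35. The longest gap is then 7 - (-7) = 14 days.

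**2. Post-baseline pain scores on file**, assuming stoppers are not recalled:

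| Sessions attended | As planned | With arrival ratings |
|---|---|---|
| 1 | 0 | 0 |
| 2 | 0 | 1 |
| 3 | 0 | 2 |
| 4 | 0 | 3 |
| 5 (and follow-up) | 2 | 6 |

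**3. Carry-forward when stopping is unrelated to response.** Assume a fraction *d* stops in each arm and would otherwise have reached the full effect. Stoppers contribute zero change, so the share of the true difference retained is 1 - *d*. Now add arrival ratings but keep carry-forward. Assume the effect builds by one fifth per session and stops are spread evenly after sessions 1-4. The last rating then reflects 0, 0.2, 0.4 or 0.6 of the effect, mean 0.3, so the share retained is (1 - *d*) + 0.3*d*.

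| *d* (assumed) | As planned | Arrival ratings, still carried forward |
|---|---|---|
| 5% | 0.95 | 0.965 |
| 10% | 0.90 | 0.93 |
| 20% | 0.80 | 0.86 |
| 30% | 0.70 | 0.79 |

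The ratings alone recover 30% of the loss, so the SAP rule has to change as well.

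**4. Stopping related to response.** Assumed: mean improvement 1.5 points (control) and 2.5 (experimental), so the true difference is 1.00; between-person SD of improvement 1.2. The carry-forward estimate is (1 - *d*E) × *m*E - (1 - *d*C) × *m*C, where *m* is the mean improvement among those observed. With 17% and 23% stopping independently of improvement, this is 0.83 × 2.5 - 0.77 × 1.5 = 2.075 - 1.155 = 0.92. When poor responders are likelier to stop, *m* shifts differently in the two arms and simulation is needed. Across assumed dropout of 14-28% and varying strength of dependence:

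| Analysis | Estimated difference (truth 1.00) |
|---|---|
| Baseline carried forward | about 0.81-0.93 |
| Baseline-adjusted, observed scores only | 0.95-0.99 |
| Arrival ratings used, recorded pain drives stopping | about 1.00 |
| Arrival ratings used, unrecorded improvement drives stopping | 0.97-0.995 |

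The shortfall is 0.07-0.19 points with carry-forward, 0.01-0.05 without it, and 0-0.03 with the ratings. These are illustrations, not bounds; step 3 already gives 0.70 for equal 30% stopping.

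**The case against.** Assessment before, after and at follow-up is a coherent design for a five-week course, and nothing in the documents contradicts it. The documents give no dropout figure, and "All participants were assessed three times, pre-treatment, post-treatment and follow-up" together with the SAP's intention-to-treat statement could mean that stoppers are recalled. If they are, the gap costs little. Recall is also the more direct remedy. The text is in the past tense, so new data collection may no longer be possible. All of this stands as a limit on the point. It does not remove it, because the SAP's substitution rule expects missing assessments and recall is not described.

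The opposing case is also right that most of the bias belongs to carry-forward. Exact recovery to 1.00 appears only when the recorded scores are what drives stopping.

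A reader might infer a large gain in precision, on the view that the outcome side rests on a single rating. Under equal correlation *r* between ratings, the baseline-adjusted variance of a mean of *k* ratings is proportional to (1 + (*k* - 1)*r*)/*k* - *r*². Going from one rating to two takes it from 0.75 to 0.50 at *r* = 0.5 and from 0.51 to 0.36 at *r* = 0.7, a cut of 33% and 29%. The documents do not support that comparison. Pain is already rated twice after treatment and both ratings enter the model. Averaging a third with them takes 0.50 to 0.417, or 0.36 to 0.31, a cut of 17% or 14%. Even that needs an averaged endpoint, which is not proposed here.

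**Conclusion.** The point holds in limited form. The 35-day gap follows directly from the schedule. For anyone lost before the end of session 5 and not recalled, the SAP enters zero change at both later time points. Under the assumptions above, replacing carry-forward yields most of the improvement. The in-course ratings add at most about 0.05 of a point when the true difference is 1.00. The case for them is that they are cheap and that no analysis can recreate them later.

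Two stronger readings should be resisted. A reader might infer that arrival ratings would cure the dropout problem. They would not: someone who stops before session 2 still has only the pre-treatment score, and pain after the last attended session stays unrecorded. A reader might also infer that the trial's estimate is biased by a known amount. The documents give no dropout rate, standard deviation or recall policy, so every figure for the estimated difference rests on assumption.

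**What to change.** In the protocol's Outcomes section, add:

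> On arrival at sessions 2, 3, 4 and 5, before the exercises, the participant writes a 0-10 pain score on a card and returns it in a closed envelope to the independent assessor.

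This keeps outcome collection separate from the treating physiotherapist. In the same place, state whether participants who stop treatment are still recalled for the two later assessments.

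In the SAP, replace carry-forward for pain with either a mixed model using all ratings or multiple imputation by arm that includes the arrival ratings. Keep post-treatment and follow-up as the outcome time points. The arrival ratings should inform missing values and not be averaged into the endpoint. If the effect built by one fifth per session, the mean over all six post-baseline ratings would carry only (0.2 + 0.4 + 0.6 + 0.8 + 1 + 1)/6 = 0.67 of the final effect.

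Cost: one number at each of four visits already attended, a sentence or two in each document, slightly more form handling, and repeated attention to pain that is equal in both arms. No extra visit or staff is needed. If data collection is already complete, only the SAP change remains available, and on the figures above it brings most of the benefit.

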Statistical Plan

Official Title: Visceral Manipulation in Patients With Chronic Low Back Pain

NCT03101020

Document Date: November, 18th 2016

Statistical Analysis Plan

Intention to treat analysis was employed when necessary, with the data from the previous evaluation repeated to substitute missing data. The Kolmogorov-Sirmonov test demonstrated normal data distribution. Thus, parametric tests were performed and the data were expressed as mean and standard deviation. Two-way analysis of variance (ANOVA) was used to compare the effects of stimulation during motor training on the main outcome variables and the Bonferroni correction for multiple comparisons was employed as the post hoc test. The dependent variables were pain intensity, lumbar mobility, general functionality and specific functionality. The independent fixed variables were treatment (baseline, posttreatment and follow-up), group (experimental group and control group) and group-treatment interaction. The Pearson correlation test verified the correlation between the outcomes of the variables. A p-value <0.05 indicated a statistically significant result. The data were organized and tabulated using the Statistical Package for Social Sciences (v.19.0).

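### If any outcome values are missing, the SAP's only rule scores a participant lost before post-treatment as unchanged, so the group difference may be biased in either direction; this is possible, not shown

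*SAP*

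**What the plan says.** The Statistical Analysis Plan handles missing outcomes in one sentence: "Intention to treat analysis was employed when necessary, with the data from the previous evaluation repeated to substitute missing data". Neither document states a missing-data assumption, another method, a sensitivity analysis, or an expected or observed dropout rate.

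The visits are set out in the protocol under Outcomes: "All participants were assessed three times, pre-treatment, post-treatment and follow-up". On timing, "post-treatment was right after the last session of treatment and the follow-up was one week after the last session of treatment". The only evaluation before post-treatment is therefore the baseline one.

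On treatment, the protocol's opening section says "Each session took 50 minutes, starting with 40 minutes of conventional physiotherapy and finishing with 10 minutes of active or placebo visceral manipulation", and also "All participants received equal treatment during the assessments and conventional therapy". Under Visceral manipulation, the placebo is given "with the same amount of time and repetitions as the experimental group".

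The analysis is a two-way ANOVA: "The independent fixed variables were treatment (baseline, posttreatment and follow-up), group (experimental group and control group) and group-treatment interaction". The SAP does not state the error term.

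**The concern.** Repeating the previous value looks harmless, but for a participant lost before post-treatment it enters baseline at both later visits, that is, a change of exactly zero. Both arms receive 40 minutes of physiotherapy per session, so improvement is plausible in both and zero change is not a neutral guess. Each arm's mean improvement is then misstated by an amount that depends on how many left and on how they would have done. Nothing in the plan makes that amount equal in the two arms. At stake is the estimated group difference in pain, the primary outcome. The same rule also applies to mobility and to both functional scales.

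**Working it through.** **Inputs from the documents.** Three visits (protocol, Outcomes); previous value repeated (SAP); group-by-visit contrasts that are differences of means (SAP). The plan has no sample size, SD, effect or dropout figure to reproduce.

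**Identity.** In one arm, let p be the share lost before post-treatment, m the mean improvement those lost would have had, and o the mean improvement of those observed.

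- Everyone measured: (1 − p)·o + p·m
- SAP rule: (1 − p)·o + p·0
- Error in the arm: −p·m

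With E for experimental and C for placebo, and plus favouring experimental:

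bias in the difference = pC·mC − pE·mE

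This holds for any dropout mechanism and any ANOVA error term, because it concerns the means. It is zero only when the two products match, which includes no dropout and no improvement among those lost.

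**Assumed inputs for size.** Pain 0–10, SD 2, correlation 0.5 between visits, improvement 2.5 in both arms under no effect. SD of change = √(2 × 2² × (1 − 0.5)) = 2. Dropout is written experimental vs placebo.

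*Random dropout, no true effect*

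- 5% vs 10%: 0.10 × 2.5 − 0.05 × 2.5 = +0.125
- 10% vs 20%: 0.50 − 0.25 = +0.25
- 10% vs 25%: 0.625 − 0.25 = +0.375
- 25% vs 10%: 0.25 − 0.625 = −0.375
- Equal rates: 0

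*Equal random dropout, true effect 1.5 (improvement 4.0 vs 2.5)*

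- 10%: 0.25 − 0.40 = −0.15, so 1.5 reads as 1.35
- 20%: 0.50 − 0.80 = −0.30, so 1.5 reads as 1.20

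*Outcome-related dropout.* If leaving correlates a with poor improvement, m = 2.5 − a × 2 × φ(z)/p, where φ(z)/p is 1.755 at p = 10%, 1.400 at 20% and 1.271 at 25%. With no true effect:

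| Setting | pC·mC | pE·mE | Bias |
|---|---|---|---|
| 10% vs 25%, exactly the least improved leave (a = 1) | 0.25 × (−0.042) = −0.011 | 0.10 × (−1.010) = −0.101 | +0.09 |
| 10% vs 25%, a = 0.5 | 0.25 × 1.229 = 0.307 | 0.10 × 0.745 = 0.075 | +0.23 |
| 10% vs 25%, a = −0.5 | 0.25 × 3.771 = 0.943 | 0.10 × 4.255 = 0.426 | +0.52 |
| 20% vs 20%, experimental a = 0.5, placebo a = −0.5 | 0.20 × 3.900 = 0.780 | 0.20 × 1.100 = 0.220 | +0.56 |

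Equal rates do not protect the comparison when the reasons for leaving differ by arm.

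**Only follow-up missing.** Here m is just the change over one week. With 20% missing in each arm, an effect constant at 1.5 stays 1.5. One waning from 1.5 to 1.0 reads as 1.0 + 0.20 × 0.5 = 1.10. The distortion is small.

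**Simulation** (30 per arm, three visits, 10,000 trials per setting) agreed with the identity within 0.015. Rejection rates with random dropout and no effect depend on the unstated error term. At 10% vs 25% they were 11.5% with a within-participant error term and 0.6% with the literal fixed-factor ANOVA. At 5% vs 10% the within-participant figure was 5.8%. Power for an effect of 1.5 at 0%, 10% and 20% equal random dropout was 85%, 71% and 58% with carry-forward and a within-participant error term, against 85%, 83% and 78% for a mixed model on observed visits.

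**The case against.** **The rule may never have acted.** The protocol says "All participants were assessed three times, pre-treatment, post-treatment and follow-up", and the SAP applies its rule only where needed. The sentence may describe the schedule or may mean complete data. If no values were missing, there is no bias. This stands and limits the point to a conditional one.

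**A large dropout gap is unlikely.** Conventional therapy is the same in both arms and the placebo is matched for spots, time and repetitions. That makes 10% vs 25% less plausible than 5% vs 10%, where the bias is about an eighth of a point and rejection is near nominal. This stands for the size. It does not remove the shrinkage of a real effect at equal dropout, or the bias when the arms differ in who leaves.

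**The mixed model can be worse.** At 10% vs 25%, if exactly the least improved leave, its simulated bias is −0.36 to −0.37 against +0.09 for carry-forward, and its rejection rate is about 12% against 7.2% for carry-forward with a within-participant error term. With opposite mechanisms at 20% vs 20% it gains little (+0.53 against +0.56). It is clearly better for random dropout (bias 0.00 against 0.38 at 10% vs 25%) and for dropout related to baseline pain (0.01 against 0.45). This stands, and is why a change of model alone is not enough.

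**Stronger readings that a reader might infer.**

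- That this trial's result is biased, or biased towards the experimental arm. The documents hold no dropout or outcome figures, and the sign can go either way.
- That the plan inflates the type I error. This depends on an error term the SAP does not state. Under the literal fixed-factor reading, rejection never exceeded 2.8% in any random-dropout setting examined, so inflation is not claimed there.

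**Conclusion.** The point holds in conditional form. If any post-treatment values are missing, the rule enters zero change for those participants, and the group difference is off by pC·mC − pE·mE. With unequal dropout this can favour either arm. With equal random dropout a real effect shrinks by about the dropout share. Over the random-dropout examples with no true effect, the bias runs from −0.375 to +0.375 points on the 0–10 scale. Every size rests on assumed dropout, improvement, SD and correlation.

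The rule also hides a range. At 10% vs 25% with an improvement of 2.5, removing up to the whole improvement from dropouts in the experimental arm only moves the difference by as much as −0.10 × 2.5 = −0.25. In the placebo arm only, it moves by as much as +0.25 × 2.5 = +0.625. The SAP reports a single point in that range, +0.375.

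Confidence is high for the algebra and moderate for any effect on this trial.

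**What to change.** First report, by arm and visit, how many outcome values are missing. If none are, say so; nothing else changes.

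If any are missing:

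1. Replace carry-forward in the primary analysis with a likelihood-based mixed model on all observed visits including baseline (group, visit, group-by-visit, within-participant correlation), or with multiple imputation by arm. Include every allocated participant in the allocated group, and state the missing-at-random assumption.
2. Add a sensitivity analysis that reduces dropouts' imputed improvement in the experimental arm only, the placebo arm only, and both, from 0 to at least the whole observed mean improvement.
3. Keep carry-forward as a separate sensitivity analysis. Removing the whole improvement in both arms reproduces it only under random dropout (0.375 and 0.375 at 10% vs 25%). With opposite mechanisms at 20% vs 20%, the shift gives 0.40 where carry-forward gives 0.56.

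**Cost.** No new data are needed. The SAP is in the past tense and already reports a result ("The Kolmogorov-Sirmonov test demonstrated normal data distribution"), so this may mean a re-analysis and not only new wording. Intervals may be wider, and missing at random cannot be tested. Because the mixed model can be further from the truth when the least improved leave, the shift analysis is part of the fix and not an optional extra.

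### The SAP's two-way ANOVA lists no participant term for three repeated visits; fitted as written, with positive within-person correlation, the group-by-visit test loses power and the visit-averaged group test is too liberal

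*SAP*

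**What the plan says.** The Protocol's Outcomes section makes this a repeated-measures design: "All participants were assessed three times, pre-treatment, post-treatment and follow-up". The visits are unevenly spaced. On treatment, the Protocol says "They were treated one time per week for five weeks". On timing, it says "Pre-treatment assessment was one week before the first session of treatment" and "post-treatment was right after the last session of treatment and the follow-up was one week after the last session of treatment". Five weekly sessions span four weeks from first to last, so baseline to post-treatment is about 1 + 4 = 5 weeks, and post-treatment to follow-up is 1 week.

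The SAP is a single paragraph. It names the method: "Two-way analysis of variance (ANOVA) was used to compare the effects of stimulation during motor training on the main outcome variables". It then lists the terms: "The independent fixed variables were treatment (baseline, posttreatment and follow-up), group (experimental group and control group) and group-treatment interaction". The factor that it calls treatment is the assessment visit. For follow-up comparisons, "the Bonferroni correction for multiple comparisons was employed as the post hoc test". The significance rule is "A p-value <0.05 indicated a statistically significant result". The same model serves all four outcomes, including the primary one, pain intensity.

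Neither document mentions a participant or random effect, a within-participant factor, a covariance structure or a sphericity correction.

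**The concern.** A two-way ANOVA with only visit, group and their interaction treats the three values from one person as three independent people. Every test then shares one pooled residual. That residual mixes two sources of variation that a repeated-measures design has to separate: differences between people, and changes within a person.

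The treatment question is whether the groups change differently, which is the group-by-visit interaction. It is a within-person comparison. If it is judged against an error that still contains the differences between people, a real effect can be missed, and a non-significant result cannot be read as absence of effect. The group main effect averages over all three visits and errs the other way, so it is declared significant too often. Because it includes the pre-treatment visit, it is also not a clean test of treatment.

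**Working it through.** The documents give no sample size, power, effect size, SD or within-person correlation, so there is no figure of the plan's own to reproduce.

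**Inputs from the documents.** Three assessments per participant (Protocol, Outcomes); visit, group and their interaction as the only listed terms (SAP); significance level 0.05 (SAP).

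**Assumed inputs.** 30 per arm; equal variances σ²; complete data; no group difference at baseline and 0.6 SD at both later visits for power; correlation ρ as shown.

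**Step 1: the error term as written.** With N participants there are 3N observations and six cell means, so the residual has 3N − 6 degrees of freedom. At 30 per arm this is 180 − 6 = 174. Its mean square has expectation σ².

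**Step 2: what it is compared with.** Under the null and equal correlation ρ:
- The interaction mean square has expectation σ²(1 − ρ), because it is built from differences within a person.
- The group mean square has expectation σ²(1 + 2ρ), because the mean of three visits has variance σ²(1 + 2ρ)/3.

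With ρ > 0, the denominator σ² is too large for the first test and too small for the second.

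**Step 3: type I error, large sample.**
- Interaction: P(χ²₂ > 5.991/(1 − ρ)). At ρ = 0.5 this is P(χ²₂ > 11.98) = exp(−5.99) = 0.0025.
- Group: 2[1 − Φ(1.96/√(1 + 2ρ))]. At ρ = 0.5 this is 2[1 − Φ(1.386)] = 0.166.

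| Equal ρ | Interaction, formula | Interaction, simulated | Group, formula | Group, simulated |
|---|---|---|---|---|
| 0 | 5.0% | about 5% | 5.0% | about 5% |
| 0.3 | 1.4% | about 1.5% | 12.1% | about 12% |
| 0.5 | 0.25% | about 0.3% | 16.6% | about 17% |
| 0.7 | 0.005% | under 0.1% | 20.6% | about 20% |

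**Step 4: interaction power at 30 per arm (simulated).** Separate runs differed by up to about two percentage points.

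| Assumed correlations | As written | Split-plot, Greenhouse-Geisser |
|---|---|---|
| Equal 0.3 | 32% | 49% |
| Equal 0.5 | 27% | 65% |
| Equal 0.7 | 20% | 88% |
| Post/follow-up 0.8, baseline with later visits 0 | 32% | 38% |
| Post/follow-up 0.8, baseline with later visits 0.2 | 30% | 46% |
| Post/follow-up 0.8, baseline with later visits 0.4 | 28% | 58% |

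The uneven spacing is a reason not to assume equal correlation. It does not supply the values in the last three rows; those are choices.

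**Step 5: do the corrected tests behave?** Across these correlation patterns, at 20, 30 and 40 per arm, group tested on between-participant error ran at 4.8–5.2%. The interaction with Greenhouse-Geisser ran at 4.5–5.1%. An uncorrected within-participant interaction test, which is what a random intercept alone gives, ran at 4.7–5.2% under equal correlation but 5.9–7.1% under the uneven patterns.

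**Step 6: what is not affected.** A group contrast at a single visit, using the pooled error, stayed at 4.8–5.4% under equal variances. That depends on the assumption: with assumed SDs of 1.5 at baseline and 2.5 at both later visits, it ran at 8.3%.

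**Step 7: a single contrast for pain, power at 30 per arm (simulated).**

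| Assumed correlations | Change score | Post-treatment adjusted for baseline (ANCOVA) |
|---|---|---|
| Post/follow-up 0.8, baseline 0 / 0.2 / 0.4 | 37 / 43 / 56% | 61 / 63 / 71% |
| Equal 0.3 / 0.5 / 0.7 | 49 / 64 / 84% | 66 / 74 / 89% |

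**The case against.** The best defence is that the SAP lists fixed variables only. A participant term is a random effect or error stratum and would not normally appear in such a list. A visit factor crossed with group and followed by Bonferroni comparisons is also a common short description of a mixed repeated-measures ANOVA. In a one-paragraph SAP, silence about the error term is weak evidence that it was absent. The SAP also speaks of stimulation with motor training, which matches nothing in the Protocol's interventions, so the paragraph may not record exactly what was fitted.

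This stands as a limit. A reader might infer that the wrong model was run; the documents do not show that. It does not remove the point, because nothing else in either document supplies the participant term, and someone following the text would get the wrong error terms.

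A reader might also infer that a positive result from this trial is likely to be false. That does not follow. Under equal variances and positive correlation, a significant interaction carries no excess false positives, and neither do single-visit group contrasts. The SAP does not say that the visit-averaged group effect decides the trial.

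It is also fair to say that every size here is assumed and that the range is too wide to bound the harm. The simulations use complete data, whereas the SAP fills gaps with the last recorded value; that repetition would tend to raise the correlation between visits. The directions need positive average correlation. They reverse at an assumed −0.2 (interaction 8.3%, group 1.2%), but positive correlation is what one expects from the same people measured over about six weeks.

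**Conclusion.** The analysis is wrong as written and should be corrected, but the finding is conditional. If the listed model was fitted and within-person correlation is positive, the interaction test is conservative and the visit-averaged group test is liberal. Those directions follow from the expected mean squares and do not depend on sample size.

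The sizes are illustrations only. At 30 per arm, 0.6 SD and equal correlation 0.3 to 0.7, the interaction loses between about a third of its power (32% against 49%) and more than three quarters of it (20% against 88%). With later visits correlated at 0.8 and baseline uncorrelated with them, the loss is small (32% against 38%). The main harm is a missed effect on the primary outcome. The over-called group effect comes second, since it should not carry the conclusion in any case. Confidence is medium, because the text does not settle which error term was used.

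**What to change.** Replace the stated model with one of these:
- a split-plot repeated-measures ANOVA, with visit as the within-participant factor and a Greenhouse-Geisser correction; or
- a linear mixed model with visit, group and visit-by-group and an unstructured within-participant covariance.

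A random intercept alone, or an uncorrected within-participant test, is not a safe substitute when the visits are this unevenly spaced. Take the Bonferroni comparisons from the chosen model, each with its own standard error. Do not rest the treatment conclusion on the visit-averaged group effect.

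If one primary contrast for pain intensity is wanted, use post-treatment pain adjusted for baseline (ANCOVA) and not the change score, which had less power in every setting examined. Label it post hoc if it was chosen after the data were seen.

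If a repeated-measures procedure was already run, one corrected sentence in the SAP is enough. If the plain two-way ANOVA was run, re-analyse all four outcomes. No new data are needed.

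The cost is that the standard error of the visit-averaged group effect grows by a factor √(1 + 2ρ), which is 1.26, 1.41 and 1.55 at ρ = 0.3, 0.5 and 0.7, so a significant group main effect may be lost. The unstructured omnibus interaction test can also have less power than the Greenhouse-Geisser one. With baseline correlation 0 and later visits at 0.8, it was slightly below even the model as written (29% against 32% at 30 per arm).
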